7.6. Exploratory Omics Analysis

Various proteomics, transcriptomics, and genomic analyses may be performed on collected data for biomarker exploration. Additional details regarding the statistical methods for these analyses will be described in a separate plan.

7.7. Safety Analyses

7.7.1 Adverse Events

All AEs will be coded using the latest version of the Medical Dictionary for Regulatory Activities. The incidence of TEAEs, organized by system organ class and frequency, will be summarized by seriousness, severity, relationship to treatment, and by treatment at onset of the TEAE. A detailed listing of serious AEs and TEAEs leading to withdrawal will also be provided.

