5.1.3 Risk/Benefit

Subjects will be informed that participation in a human PK-PD study like the present one cannot be of benefit to healthy volunteers. Nevertheless, the information from the physical examination, vital sign measurements, and ECG results may be shared with the subject's personal physician if this is the subject's choice. Subjects will be informed that it is also their choice to inform their personal physician that they are participating in this research study.

Subjects will be informed that their contribution to the study is of major importance to agencies like the U.S. FDA for helping this agency better evaluate biomarkers. However, since this is a study involving healthy volunteers, subjects will be informed that they have the alternative not to participate.

Subjects will be informed that they may be exposed to risks associated with the pharmacological properties of the investigational product and the study procedures. The following summary of potential AEs for the study drugs will be provided to and discussed with the subjects:

1. Evolocumab (1)

- Hypersensitivity reactions: Angioedema, rash, and urticaria have occurred.
- Common adverse reactions (> 5% of patients treated with REPATHA and occurring more frequently than placebo in previous clinical trials):
 nasopharyngitis, upper respiratory tract infection, influenza, back pain, and injection site reactions, diabetes mellitus.

2. Alirocumab (2)

- Hypersensitivity reactions (e.g., pruritus, rash, urticaria), including some serious events (e.g., hypersensitivity vasculitis and hypersensitivity reactions requiring hospitalization).
- Commonly occurring adverse reactions (≥5% of patients treated with PRALUENT and occurring more frequently than with placebo in previous clinical trials) are nasopharyngitis, injection site reactions, and influenza.

The study drugs will not be administered to anyone who is pregnant. All women must take a pregnancy test before receiving any study drug in this study. All woman of childbearing potential enrolled on this study will be informed that they must use effective birth control methods (abstinence, intrauterine device, and contraceptive foam and a condom [i.e., double-barrier method]) during treatment. Subjects will be informed that they must notify the investigator if they or their female partners become pregnant during the course of the study.

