5.6.3 Study Periods

This is a randomized, placebo-controlled, single-dose, parallel arm study. Healthy subjects will be randomized to four dose groups (low, intermediate low, intermediate high, and high) of each drug (evolocumab and alirocumab) or placebo. Subjects assigned to Groups A, B, E, and F will be kept in the study for 42 days. Subjects assigned to Groups C and G will be kept in the study for 56 days, and the remaining subjects (Groups D, H, I) will remain in the study for 84 days.

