5.7.4.1 Adverse Events

5.7.4.1.1 Adverse Event Definitions

An AE is defined as any untoward and/or unintended sign, including an abnormal clinical laboratory finding, symptom, or disease temporally associated with the use of a study drug, whether or not considered related to the study drug. Events or conditions that increase in frequency or severity during or as a consequence of use of a drug in human clinical trials will also be considered AEs.

A treatment-emergent adverse event (TEAE) is defined as an AE that begins after study drug administration.

An unexpected AE is any AE having a specificity or severity not consistent with the current investigator's brochure for the study drug(s).

A serious adverse event (SAE) is defined as any AE occurring at any dose that meets the following criteria:

- Results in death,
- Is life threatening,
- Requires hospitalization or prolongation of existing hospitalization,
- Results in persistent or significant disability or incapacity,
- Results in a congenital anomaly/birth defect due to exposure prior to conception or during pregnancy, or
- Is an important medical event that may not meet the previous criteria but, based upon appropriate medical judgment, jeopardizes the subject or requires medical or surgical intervention to prevent one of the outcomes listed previously.

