5.7.4.1.2 Adverse Event Reporting

The recording of AEs will begin after the subject signs the informed consent form and will continue until discharge (or early termination). All AEs, whether serious or nonserious and whether or not related to the study drug, must be recorded in the eCRF. Study subjects will be instructed to warn study staff if he or she has any unexpected symptoms. In addition, all subjects will receive a reminder telephone call approximately 24 hours before Check-in.

Any SAE (whether expected or unexpected) must be entered into the eCRF system and reported by facsimile to the medical monitor or designee using the SAE Reporting Form within 24 hours of the investigator or study clinic staff becoming aware of the event. It is the responsibility of the investigator to report all SAEs to the medical monitor, to provide the most complete report possible, and to assess each SAE for its relationship to the study drug. The investigator is responsible for obtaining follow-up information on all SAEs and submitting follow-up SAE data. Any unexpected SAEs must be reported promptly to the investigator's IRB as per the IRB's requirements.

In the event of a fatal or life-threatening SAE, the sponsor will notify the appropriate FDA authorities by telephone or facsimile within 7 calendar days of receipt of the report. The sponsor will follow all 7-day alert reports with a written report within 10 working days of receipt of the case. Serious AE cases that concern nonfatal, nonlife-threatening events that are unexpected and at least possibly related to the study drug will be submitted in writing to the FDA within 10 working days of receipt.

Furthermore, any AEs that are not expected, occur at a higher frequency, or would require modification of the study protocol and/or informed consent must be reported to the FDA within 10 working days.

Adverse events that are assessed by the investigator as possibly or probably related to the study drug will be followed until they resolve or stabilize. All SAEs will be followed until resolution.

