5.9.8 Safety Analyses

5.9.8.1 Adverse Events

All AEs will be coded using the latest version of the Medical Dictionary for Regulatory Activities. The incidence of TEAEs, organized by system organ class and frequency, will be summarized by seriousness, severity, relationship to treatment, and by treatment at onset of the TEAE. A detailed listing of serious AEs and TEAEs leading to withdrawal will also be provided.

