3.1. Study Design

This is a randomized, double-blind, placebo-controlled, single-dose, parallel arm, pilot study. Healthy subjects will be randomized to one of four dose groups (low, intermediate low, intermediate high, and high) for each drug (evolocumab or alirocumab) or placebo (See Table 1). The study will be conducted at one center in the United States (Spaulding Clinical Research unit in West Bend, Wisconsin).

All subjects will be sampled daily for the first week. Subjects in groups A, B, E, and F will follow the schedule of events through day 42. Subjects in groups C and G will follow the schedule of events through day 56. Subjects in groups D, H, and I will follow the schedule of events through day 84. Each treatment group should include equal representation of male and female subjects.

Table 1: Study Treatment Groups

Subjects (n)	Treatment Group	Drug
8	A	Evolocumab low (21 mg) subcutaneously (SC)
8	B	Evolocumab intermediate low (35 mg) SC
8	C	Evolocumab intermediate high (70 mg) SC
8	D	Evolocumab high (140 mg) SC
8	E	Alirocumab low (15 mg) SC
8	F	Alirocumab intermediate low (25 mg) SC
8	G	Alirocumab intermediate high (50 mg) SC
8	H	Alirocumab high (100 mg) SC
8	I	Placebo SC

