7.7.3 Vital Sign Measurements

Vital sign measurements and changes from Baseline will be summarized using descriptive statistics (number of subjects, mean, SD, minimum, median, and maximum) by treatment and time point.

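### TEAE incidence is tabulated by treatment over 42, 56 or 84 days of follow-up, so shorter-followed arms look safer than placebo and incidence rises with dose without any drug effect

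*SAP*

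**What the plan says.** SAP 7.7.1 plans to report TEAE incidence by system organ class and frequency, and states that it "will be summarized by seriousness, severity, relationship to treatment, and by treatment at onset of the TEAE". Protocol 5.9.8.1 has the same rule, including "by treatment at onset of the TEAE".

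The event definition is in Protocol 5.7.4.1.1: "A treatment-emergent adverse event (TEAE) is defined as an AE that begins after study drug administration". It sets a start but no end. Under Protocol 5.7.4.1.2, recording runs from consent to the subject's discharge or early termination.

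Discharge depends on the arm. Protocol 5.6.3 says: "Subjects assigned to Groups A, B, E, and F will be kept in the study for 42 days". The same section keeps C and G for 56 days. SAP 3.1 adds: "Subjects in groups D, H, and I will follow the schedule of events through day 84". Groups D and H are the high doses and I is placebo.

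The safety population in SAP section 5 is all dosed subjects, whatever their length of follow-up. Neither document gives a common observation window, a subject-time denominator, a time-to-onset summary or a caveat on unequal follow-up for the TEAE table.

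**The concern.** A cumulative proportion depends on how long subjects are watched. In this design, watching time is tied to treatment: a 42-day arm has half the time at risk of placebo, and a 56-day arm two thirds. Within each drug, follow-up by rising dose is 42, 42, 56 and 84 days.

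A by-treatment table in a placebo-controlled, four-dose study invites two readings: active against placebo, and trend across dose. Both are distorted. Events that can start at any time will be under-counted in the low and intermediate arms relative to placebo, and the same shortfall adds an upward step across dose. A real excess in a short-follow-up arm can be hidden.

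This matters for the kind of event expected. Protocol 5.1.3 lists for evolocumab "nasopharyngitis, upper respiratory tract infection, influenza, back pain, and injection site reactions, diabetes mellitus", and for alirocumab a similar but shorter list. Infections and back pain can begin in any week; injection-site reactions cluster near dosing and are nearly unaffected.

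Vital signs do not share the problem, because SAP 7.7.3 summarises them "by treatment and time point".

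**Working it through.** **Inputs.** Follow-up T = 42, 56 or 84 days (Protocol 5.6.3, SAP 3.1), treating Day T as T days at risk. Eight subjects per arm (SAP 3.2). The documents give no AE rate, so there is no planned figure to reproduce. I assume the same hazard in every arm (no drug effect), with h = 0.25%, 0.5% or 1% per day on average over 84 days.

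**Time at risk per arm if all eight complete.** 8 × 42 = 336, 8 × 56 = 448, 8 × 84 = 672 subject-days.

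**Constant hazard.** Expected incidence is 1 − exp(−hT). For h = 0.005: 1 − exp(−0.21) = 18.9%, 1 − exp(−0.28) = 24.4%, 1 − exp(−0.42) = 34.3%.

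| h per day | 42 days | 56 days | 84 days | Gap, 42-day arm v placebo | Gap in subjects of 8 |
|---|---|---|---|---|---|
| 0.25% | 10.0% | 13.1% | 18.9% | 9 points | 0.7 |
| 0.5% | 18.9% | 24.4% | 34.3% | 15 points | 1.2 |
| 1% | 34.3% | 42.9% | 56.8% | 23 points | 1.8 |

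**Events clustered early.** Let a share f of the 84-day cumulative hazard fall in the first 7 days and the rest be uniform. Cumulative hazard at T is 84h × [f + (1 − f)(T − 7)/77]. For h = 0.005 and f = 0.5 at 42 days: 0.42 × (0.5 + 0.5 × 35/77) = 0.305, so incidence is 26.3% against 34.3% at 84 days.

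| Share in week 1 | Gap at h = 0.25% | 0.5% | 1% |
|---|---|---|---|
| f = 0.5 | 5 points | 8 points | 11 points |
| f = 0.75 | 2 points | 4 points | 5 points |

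The direction does not depend on h or f. The gap between the 42-day arms and placebo vanishes only if no TEAE starts after Day 42.

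**Masking.** Under constant hazard, 2h × 42 = 1.5h × 56 = h × 84. A true doubling of the rate in a 42-day arm, or a 1.5-fold rate in a 56-day arm, therefore gives the same expected incidence as placebo.

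**What one table of 8 against 8 would show.** Independent binomials, one 42-day arm against placebo, constant hazard:

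| h per day | Fewer affected than placebo | Tie | More affected |
|---|---|---|---|
| 0.25% | 0.557 | 0.260 | 0.182 |
| 0.5% | 0.665 | 0.177 | 0.158 |
| 1% | 0.752 | 0.130 | 0.119 |

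The probability of fewer falls to 0.46, 0.53 and 0.58 with f = 0.5, and to 0.42, 0.46 and 0.49 with f = 0.75. A reader who scans all four 42-day arms (n = 32) against the three 84-day arms (n = 24) sees the lower proportion in the 42-day arms with probability 0.81, 0.89 or 0.95 under constant hazard. The plan does not call for that pooled comparison.

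**A rate alone does not repair it.** With h = 0.005 and f = 0.5, the expected rate is 0.305/42 = 0.73 per 100 subject-days at 42 days, against 0.42/84 = 0.50 at 84 days. The bias now runs the other way. A common window gives equal expected incidence in all arms under no drug effect, whatever the shape of the hazard over time.

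**The case against.** The strongest case against concerns weight. Safety is neither an objective nor an endpoint, no decision rule or test uses TEAE incidence, and the table is descriptive. All data are listed, TEAEs are also split by severity and relationship, and the SAP itself states follow-up per arm, so a careful reader could make a Day 42 count from the listing. All of this is true. It lessens the harm, but leaves the planned by-treatment table biased.

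The effect is small in subjects: 0.7 to 1.8 of 8 under constant hazard, and 0.2 to 0.9 with early clustering, which is plausible after a single dose and a week in house. This stands, and a single table may not show the gap. The hazards are assumptions throughout.

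The dose trend is a step and not a steady slope, because the two lowest doses share 42 days. A non-decreasing pattern across the four doses, with the top above the bottom, appears within a drug about 25% of the time under constant hazard, against 11% to 15% when all four arms have a 42-day window. That qualifies the trend but does not remove it.

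Protocol 5.1.3 lists the infections as reactions more frequent than on placebo, not as background events. This is correct. They serve here only as events whose onset is not confined to the days after dosing.

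Finally, a common window does not make a real doubling reliably visible at this sample size: placebo would still tie with or exceed the doubled arm in 25% to 44% of tables. The fix removes the bias; it does not add precision.

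**Conclusion.** The concern holds. As written, the plan gives a TEAE table in which the low and intermediate doses are expected to look safer than placebo, and incidence to rise with dose above the two lowest doses, without any drug effect. The direction follows from the documents alone, provided that some events start after Day 42 (after Day 56 for groups C and G). The size rests on assumed hazards: 9 to 23 points for a 42-day arm against placebo under a constant hazard of 0.25% to 1% per day, and 2 to 11 points if half to three quarters of the hazard falls in week 1. High dose against placebo is a fair comparison, with 84 days in each. Because the analysis is descriptive and the arms are small, this should be corrected, but it does not threaten the study's main purpose.

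**What to change.** In SAP 7.7.1, define the by-treatment comparative TEAE table as subjects with TEAE onset from dosing through Day 42 in all nine arms, and show the number followed to Day 42 in each arm.

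Add a full-period table, labelled descriptive, with events per 100 subject-days and the subject-days observed per arm. Do not rely on the rate table alone, for the reason shown in the working.

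The cost is one extra table and one or two sentences in the SAP. The Day 42 table leaves out later events in C, D, G, H and I; these remain in the full-period table and the listings. No visit, dose, sample or data collection changes.

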7.7.2 Clinical Laboratory Tests

Clinical laboratory results (hematology, serum chemistry, and urinalysis) will be summarized using descriptive statistics (number of subjects, mean, SD, minimum, median, and maximum). Clinical laboratory results will be classified as normal or abnormal, according to the reference ranges of the individual parameter. No statistical testing will be performed on clinical laboratory data.

7.7.3 Vital Sign Measurements

Vital sign measurements and changes from Baseline will be summarized using descriptive statistics (number of subjects, mean, SD, minimum, median, and maximum) by treatment and time point.

7.7.4 Safety 12-lead Electrocardiograms

The incidence of pathological ECG interpretive statements at Baseline and during treatment will be assessed among the treatments.

7.7.5 Physical Examinations

Physical examination findings will be presented in a data listing, and abnormal physical examination findings will be recorded as AEs.

7.7.6 Other Safety Data

All concomitant medication usage and medications that changed in daily dose, frequency, or both since the subject provided informed consent will be summarized for each subject.

8. Data Quality Assurance

Completed eCRFs are required for each subject randomly assigned to study drug. Electronic data entry will be accomplished through the ClinSpark[®] remote electronic data capture system, which allows for on-site data entry and data management. This system provides immediate, direct data transfer to the database, as well as immediate detection of discrepancies, enabling site coordinators to resolve and manage discrepancies in a timely manner. Each person involved with the study will have an individual identification code and password that allows for record traceability. Thus, the system, and subsequently any investigative reviews, can identify coordinators, investigators, and individuals who have entered or modified records.

Furthermore, the investigator retains full responsibility for the accuracy and authenticity of all data entered into the electronic data capture system. The completed dataset and their associated files are the sole property of the sponsor and should not be made available in any form to third parties, except for appropriate governmental health or regulatory authorities, without written permission of the sponsor.

Attachment A. Pharmacokinetic, Pharmacodynamic, and Biomarker Sample Collection Schedule

Pharmacokinetic Sample Collection

Pharmacokinetic blood samples (5 mL) for determination of evolocumab or alirocumab concentration will be collected at the following time points:

- Day 1: 0 (pre-dose), 0.5, 1, 2, 3, 4, 6, 8, 12, 24 h
- Day 2, 3, 4, 5, 6, 7, 10, 14, 21, 28, 35, 42, 56, 70, 84

Blood samples will be collected by direct venipuncture or by inserting an IV catheter into the subject's forearm region. Each blood sample will be labeled with subject number, study number, study day, time point, event, and a barcode that matches that belonging to the subject.

Pharmacodynamic Sample Collection

Blood samples (5 mL) for primary pharmacodynamic biomarker (peripheral blood LDL-C) and secondary pharmacodynamic biomarker (peripheral blood ApoB) assessment will be collected at the following time points:

- Screening (Day -21 to -2)
- Day -1 (check-in)
- Day 1: 0 (Pre-dose) and 24 h (Day 2)
- Day 3, 4, 5, 7, 10, 14, 21, 28, 35, 42, 56, 70, 84

Blood samples will be collected by direct venipuncture or by inserting an IV catheter into the subject's forearm region. Each blood sample will be labeled with subject number, study number, study day, time point, event, and a barcode that matches that belonging to the subject.

Exploratory PD Biomarkers

Exploratory PD biomarkers will be evaluated using plasma proteomics and small RNA transcriptomics. Whole blood samples (5 mL) will be collected and processed for plasma at the following time points:

- Day -1 (check-in)
- Day 1: 0 (pre-dose), 0.5, 1, 2, 3, 4, 6, 8, and 12 h; 24 h (Day 2)
- Day 3, 4, 5, 6, 7, 7, 10, 14, 21, 28, 35, 42, 56, 70, 84

Blood samples will be collected by direct venipuncture or by inserting an IV catheter into the subject's forearm region. Each blood sample will be labeled with subject number, study number,

study day, time point, event, and a barcode that matches that belonging to the subject. All blood samples will be processed for preparation of plasma.

Attachment B. Randomization Schedule

Subjects will enter the study clinic for check-in procedures the day before study drug administration of the first period (Day -1). All study drugs will be administered subcutaneously. On Day 1, subjects will receive their assigned treatment according to the randomization schedule generated by the project biostatistician and provided to designated unblinded recipients (i.e., pharmacist) at the clinical site.

Treatment Group	Drug
A	Evolocumab low (21 mg)
B	Evolocumab intermediate low (35 mg)
C	Evolocumab intermediate high (70 mg)
D	Evolocumab high (140 mg)
E	Alirocumab low (15 mg)
F	Alirocumab intermediate low (25 mg)
G	Alirocumab intermediate high (50 mg)
H	Alirocumab high (100 mg)
I	Placebo
